12.5. Appendix 5: Reporting Standards for Missing Data

12.5.1. Premature Withdrawals

Element	Reporting Detail
General	
 Subject study treatment completion is defined as if the participant has taken all doses of the study treatment and completed the TOC Visit. Participants who discontinue study treatment will not be considered withdrawn from the study and should attend the TOC and Follow-up Visits as applicable. Subject study completion (i.e. as specified in the protocol) is defined as if the participant has completed all study visits including the Follow-up Visit. Withdrawn subjects may be replaced in the study. All available data from participants who were withdrawn from the study will be listed and all available planned data except for efficacy will be included in summary tables and figures, unless otherwise specified.

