8.3. Lost to Follow-Up

A participant will be considered lost to follow-up if he or she repeatedly fails to return for scheduled visits and is unable to be contacted by the study site.

The following actions must be taken if a participant fails to return to the clinic for a required study visit:

- The site must attempt to contact the participant and reschedule the missed visit as soon as possible and counsel the participant on the importance of maintaining the assigned visit schedule and ascertain whether or not the participant wishes to and/or should continue in the study.
- Before a participant is deemed lost to follow-up, the investigator or designee must make every effort to regain contact with the participant (where possible, 3 telephone calls and, if necessary, a certified letter to the participant's last known mailing address or local equivalent methods). These contact attempts should be documented in the participant's medical record.
- Should the participant continue to be unreachable, he/she will be considered to have withdrawn from the study with a primary reason of lost to follow-up.

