9.1.1.1. Microbiological Outcome and Response

- The microbiological outcome and response to study treatment will be determined by prespecified programmed algorithm for each participant/qualifying uropathogen.
- The microbiological outcome is determined by comparing the baseline culture results to the culture results at each subsequent visit. The corresponding microbiological response “by qualifying uropathogen” is then assigned. The criteria of microbiological outcome and response are shown in [Table 4](#), [Table 5](#), and [Table 6](#).
- Participant level microbiological success refers to participants who have been deemed a “microbiological success” for all their “qualifying baseline uropathogen” microbiological responses.
- All other combinations are deemed failures for participant level microbiological response.
- Participants who withdraw from the study prior to TOC or Follow-Up Visits will be considered not achieving success as the microbiological response. Microbiological outcome will be derived and listed at early termination visit.
- Microbiological outcome and response along with the 95% Clopper-Pearson CI for the percentage of microbiological response will be summarized for qualifying uropathogens isolated at baseline using the groups listed below at the On-therapy, TOC, and Follow-up visits using counts and percentages. Participant level microbiological response and 95% Clopper-Pearson CI will be summarized within the same table. The necessity of these categories will depend on the uropathogens that are recovered. Any additional uropathogens present in 10 or more participants will be

summarized separately. Additional uropathogens present in less than 10 participants will be grouped into the combined categories (eg, other beta-hemolytic streptococci).

- *Escherichia coli*
 - Quinolone-resistant *E. coli*
 - Extended spectrum beta-lactamase (ESBL) producing *E. coli*
 - Multidrug-resistant (MDR) *E. coli*
- Other gram-negative bacilli
- *Staphylococcus aureus*
- *Staphylococcus saprophyticus*
- Coagulase-negative staphylococci
- Beta-hemolytic streptococci
- Viridans streptococci
- *Enterococcus* spp.
- *Gardnerella vaginalis*
- *Aerococcus urinae*
- Other Gram-positive uropathogens
- A participant will be counted multiple times under an uropathogen category if multiple qualifying uropathogens within that uropathogen category are isolated at baseline for the participant.

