9.1.1.3. Clinical Outcome and Response

- Clinical signs and symptoms of acute cystitis will be recorded by site staff based on participant interview using the scoring system.
- The clinical signs and symptoms include at least dysuria, frequency, urgency, and lower abdominal or suprapubic pain. The clinical signs and symptoms will be scored from 0 to 3.
- At Baseline, the participant must present with at least 2 signs and symptoms and have a total cumulative symptom score ≥ 2 . At TOC, success is recorded as normal presentation of signs and symptoms with a total cumulative symptom score of zero and no new signs and symptoms of the infection under study.
- The investigator will determine the clinical outcome by comparing the signs and symptoms of acute cystitis at the On-Therapy (Days 2 through 5 only), TOC, and Follow-up Visits to those present at Baseline. The clinical response based on investigator-determined clinical outcome will be programmatically derived using the criteria in [Table 7](#).
- The sponsor-determined clinical outcome and response will be programmatically determined by comparing the scores of the signs and symptoms of acute cystitis at the On-Therapy (Days 2 through 5 only), TOC, and Follow-up Visits to those present at Baseline as shown in [Table 7](#).
- Participants who withdraw from the study prior to TOC or Follow-Up Visits will be considered not achieving success as the clinical response at TOC or Follow-Up Visits. The investigator- and sponsor-determined clinical response and outcome at Early Termination visit will only be listed.
- Clinical response (success or failure) will be determined at TOC or Follow-Up visits for each participant. A “success” clinical response is defined as if the clinical outcome for all qualifying uropathogens is “clinical success” for the visit, otherwise a “failure” clinical response will be assigned.
- Clinical cure is defined in [Table 8](#) and will be programmatically derived at the On Therapy (Days 2 through 5), TOC, and Follow-up Visits. If a participant does not meet clinical cure at TOC visit, the participant will not be considered as clinical cure at Follow-up visit.

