
 • Refusal to consent to a clinical examination or failure to attend the On-Therapy visit (Days 2 through 5 only) 	
 • Unable to Determine 	
 • Not applicable
Test-of-Cure Visit		

 • Resolution of signs and symptoms of acute cystitis (total cumulative score is zero) present at Baseline (and no new signs or symptoms) and no use of other antimicrobial therapy 	
 • Clinical success 	
 • Success

 • Persistence of signs and symptoms of infection (total cumulative score is >0), reappearance of signs and symptoms, or use of other antimicrobial therapy for the current infection 	
 • Clinical failure 	
 • Failure

 • Refusal to consent to a clinical examination or failed to attend the TOC Visit 	
 • Unable to determine 	
 • Failure

Follow-up Visit		

 Resolution of signs and symptoms of acute cystitis demonstrated at the TOC Visit persist at the Follow-up Visit (total cumulative score is zero) (and no new signs and symptoms) and no use of other antimicrobial therapy 	
 Sustained clinical success 	
 Success

 Resolution of signs and symptoms of acute cystitis at the Follow-up Visit (total cumulative score is zero) and no use of other antimicrobial therapy, but lack of clinical success at the TOC Visit 	
 Delayed clinical success 	
 Failure

 Persistence of signs and symptoms of infection (total cumulative score is >0), reappearance of signs and symptoms, or use of other antimicrobial therapy for the current infection 	
 Clinical failure 	
 Failure

 Signs and symptoms of acute cystitis absent at the TOC Visit re-occur at the Follow-up Visit and no use of other antimicrobial therapy 	
 Clinical recurrence 	
 Failure

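### SAP 12.5.1 by default keeps efficacy data of withdrawn participants out of tables and figures, and no sentence expressly retains results observed before the withdrawal

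*SAP*

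**What the plan says.** SAP 12.5.1 (Premature Withdrawals) gives the general rule for participants withdrawn from the study. All their data are listed, and "all available planned data except for efficacy will be included in summary tables and figures, unless otherwise specified". The same section says that stopping study treatment alone is not withdrawal, and that completing the study requires the Follow-up Visit.

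Protocol 8.3 says of a participant who cannot be reached that "he/she will be considered to have withdrawn from the study with a primary reason of lost to follow-up". Someone lost after TOC but before Day 28 is therefore withdrawn.

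SAP Section 9 has its own rules for withdrawals:
- Microbiological response (9.1.1.1): "Participants who withdraw from the study prior to TOC or Follow-Up Visits will be considered not achieving success as the microbiological response".
- Clinical response (9.1.1.3): "Participants who withdraw from the study prior to TOC or Follow-Up Visits will be considered not achieving success as the clinical response". The sentence goes on to name both visits.
- Early-termination results: "Microbiological outcome will be derived and listed at early termination visit", and "The investigator- and sponsor-determined clinical response and outcome at Early Termination visit will only be listed".
- A missed TOC visit (Table 7): "Refusal to consent to a clinical examination or failed to attend the TOC Visit" is assigned unable to determine, with response failure.

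The ITT and micro-ITT definitions (Protocol 10.2, SAP 4) do not make withdrawal a reason for exclusion. Protocol 10.3.3 plans micro-ITT summaries of outcomes on Days 2 to 5, at TOC and at Follow-up without such an exclusion. The SAP's list of changes to the protocol analyses (2.1) does not mention one.

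**The concern.** The general rule removes efficacy from the displays, and the specific rules restore only part of it. They deal with response at TOC and Follow-up. They are silent on results that exist because the participant attended and was assessed before leaving: daily microbiological and clinical outcomes, culture counts, symptom scores, clinical cure, and a TOC result already in hand.

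If a programmer applies 12.5.1 as written, whether a woman's TOC or Day 3 result is summarised depends on whether she attended a later visit. That can move a rate in either direction, according to who is lost. In a small open-label study the choice should be closed before anyone tabulates the outcomes.

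**Working it through.** The plan states no figure for this handling, so there is none to reproduce. Its only sample-size justification (Protocol 10.1) concerns precision of plasma AUC and Cmax and does not bear on the point. The check has two parts.

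**1. Which rule governs which data, for a participant withdrawn from the study**

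| Data | 12.5.1 default | Express override in Section 9? |
|---|---|---|
| Response at a TOC or Follow-up visit missed through withdrawal | Out | Yes: non-success (9.1.1.1, 9.1.1.3; Tables 5 to 7) |
| Early-termination results | Out | Not needed: Section 9 also makes them listing-only |
| Observed Days 2 to 5 outcomes | Out | None |
| Culture counts (Table 2.2, Figure 2.2) | Out | None |
| Symptom scores (Table 2.8, Figure 2.3) | Out | None |
| Clinical cure (Table 2.9, Figure 2.1) | Out | None |
| TOC result observed, lost before Day 28 | Out | Unclear |

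The last row is unclear because the 9.1.1.1 and 9.1.1.3 sentences name TOC and Follow-up together and do not tie the failure to the visit that was missed. An observed TOC success followed by loss before Day 28 can therefore be programmed in three ways:
- kept as a success (the TOC rows of Tables 5 and 7);
- excluded (12.5.1);
- set to failure at TOC (a broad reading of the withdrawal sentences).

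The combination is also uneven within a display. A woman lost between Day 5 and TOC would count as a failure at TOC, while her observed Days 2 to 5 results were left out.

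**2. Size**

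The documents give neither the micro-ITT size nor a withdrawal rate. About 20 is the target for PK-evaluable participants, from 25 to 30 enrolled. Assumptions: micro-ITT N of 10, 15 or 20; 80% observed TOC success (8, 12 or 16 successes); w = 1 to 3 of the successes lost after TOC and before Day 28.

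With x observed successes, keeping gives x/N, excluding gives (x − w)/(N − w), and failure at TOC gives (x − w)/N. Intervals are 95% Clopper-Pearson, the SAP's method: for k successes out of n, the lower limit is the 0.025 quantile of Beta(k, n − k + 1) and the upper limit is the 0.975 quantile of Beta(k + 1, n − k).

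| N, w | Kept | Excluded | Failure at TOC |
|---|---|---|---|
| 20, 1 | 16/20 = 80.0% (56.3–94.3) | 15/19 = 78.9% (54.4–93.9) | 15/20 = 75.0% (50.9–91.3) |
| 20, 2 | 16/20 = 80.0% (56.3–94.3) | 14/18 = 77.8% (52.4–93.6) | 14/20 = 70.0% (45.7–88.1) |
| 20, 3 | 16/20 = 80.0% (56.3–94.3) | 13/17 = 76.5% (50.1–93.2) | 13/20 = 65.0% (40.8–84.6) |
| 15, 2 | 12/15 = 80.0% (51.9–95.7) | 10/13 = 76.9% (46.2–95.0) | 10/15 = 66.7% (38.4–88.2) |
| 10, 2 | 8/10 = 80.0% (44.4–97.5) | 6/8 = 75.0% (34.9–96.8) | 6/10 = 60.0% (26.2–87.8) |

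If the women lost are observed TOC failures, exclusion works the other way. With N = 20, 16 successes and 3 of the 4 failures lost, it gives 16/(20 − 3) = 16/17 = 94.1% (71.3–99.9) instead of 80.0%.

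**The case against.** A reader might infer that 12.5.1 contradicts the failure rule, so that participants who withdraw before TOC vanish from the TOC denominator and the success rate rises. The documents do not support that. The 12.5.1 sentence yields to anything specified elsewhere, and 9.1.1.1 and 9.1.1.3 do specify it. Tables 5 to 7 and the therapeutic response rule (9.1.1.4) agree. Read as a whole, the plan keeps these women as failures at the visits they miss.

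A reader might also infer that participants who stop for lack of effect disappear from the on-therapy summaries. Protocol 8.1 lists lack of efficacy as a reason for stopping treatment and says that such participants are not withdrawn from the study; SAP 12.5.1 repeats that stopping treatment is not withdrawal. Participants are also confined through Day 5, and anyone discontinuing in that period completes the Day 5 assessments.

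The strongest remaining defence is that Section 9 plans by-visit summaries on ITT or micro-ITT sets that include withdrawals and gives absent results an unable-to-determine category, so keeping observed data is the natural intention. The efficacy exception may have been meant only for early-termination data. The first part has force: it is why this is a defect of wording and not a settled exclusion. But those summary rules do not mention withdrawn participants, and the unable-to-determine category covers results that are absent, not results that exist. The early-termination explanation fits poorly. The exception is carved out of planned data, the Schedule of Activities has no early-termination visit, and Section 9 already restricts those results to listings.

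It is also fair that ITT listings 12 to 16 keep participant-level efficacy results visible, and that SAP 12.5.2 requires exclusions from summaries to be documented with reasons. That limits the harm but does not settle what the tables contain.

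**Conclusion.** The point holds in a limited form. The stated default excludes efficacy data of withdrawn participants from displays, the overrides reach only TOC and Follow-up response, and results observed before withdrawal have no express protection. With 20 in the micro-ITT set and 2 TOC successes lost before Day 28, the three readings span 70.0% to 80.0%. Losing 3 observed TOC failures under exclusion would give 94.1%. These sizes rest on an assumed set size, success rate and number of losses, and the confidence intervals are far wider than the differences in most cases. Efficacy is exploratory and no hypothesis is tested. The primary PK analysis and the sample size do not change. The amendment is still worth making, because the rule as written lets later attendance decide which observed results are summarised.

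**What to change.** In SAP 12.5.1, delete the three-word efficacy exception and add a short statement:
- Efficacy results observed at scheduled visits before withdrawal stay in the by-visit summaries of each display's own population (micro-ITT or ITT; Tables 2.5, 2.6, 2.8 and 2.9 use ITT).
- Visits after withdrawal are unable to determine, with response failure at TOC and Follow-up as in Section 9.
- Withdrawal after an attended TOC visit does not change the TOC response.
- Only early-termination visit results are confined to listings.

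The cost is a few lines of SAP text, to be settled before database freeze. No data collection, sample size or PK analysis changes. Reported rates may move slightly in either direction compared with a literal application of the current text.

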12.5.2. Handling of Missing Data

Element	Reporting Detail
General	
 Missing data occurs when any requested data is not provided, leading to blank fields on the collection instrument: 
 These data will be indicated by the use of a “blank” in subject listing displays. Unless all data for a specific visit are missing in which case the data is excluded from the table. Answers such as “Not applicable” and “Not evaluable” are not considered to be missing data and should be displayed as such.
Outliers	
 Any participants excluded from the summaries and/or statistical analyses will be documented along with the reason for exclusion in the clinical study report.

12.5.2.1. Handling of Missing and Partial Dates

Element	Reporting Detail
General	
 Partial dates will be displayed as captured in subject listing displays.
Adverse Events	
 The eCRF allows for the possibility of partial dates (i.e., only month and year) to be recorded for AE start and end dates; that is, the day of the month may be missing. In such a case, the following conventions will be applied for calculating the time to onset and the duration of the event: 
 Missing Start Day: First of the month will be used unless this is before the start date of study treatment; in this case the study treatment start date will be used and hence the event is considered On-treatment as per Appendix 3: Study Phases and Treatment Emergent Adverse Events. Missing Stop Day: Last day of the month will be used, unless this is after the stop date of study treatment; in this case the study treatment stop date will be used. Completely missing start or end dates will remain missing, with no imputation applied. Consequently, time to onset and duration of such events will be missing. Adverse events with entirely missing or unknown start dates will be assumed to be on-treatment for reporting.
Concomitant Medications/	
 Partial dates for any concomitant medications recorded in the CRF will be imputed using the following convention:

Element	Reporting Detail
Medical History	

○ If the partial date is a start date, a '01' will be used for the day and 'Jan' will be used for the month
○ If the partial date is a stop date, a '28/29/30/31' will be used for the day (dependent on the month and year) and 'Dec' will be used for the month.
● The recorded partial date will be displayed in listings.

12.6. Appendix 6: Values of Potential Clinical Importance

12.6.1. ECG

ECG Parameter	Units	Potential Clinically Important Range	
		Lower	Upper
Absolute			
Absolute QTc Interval	msec	> 450 ^[1]	
		> 450 ^[2]	≤ 479 ^[2]
		≥ 480 ^[2]	≤ 499 ^[2]
		≥ 500 ^[2]	
Absolute PR Interval	msec	< 110 ^[1]	> 220 ^[1]
Absolute QRS Interval	msec	< 75 ^[1]	> 110 ^[1]
Change from Baseline			
Increase from Baseline QTc	msec	> 30 ^[1]	
		> 30 ^[2]	≤ 59 ^[2]
		≥ 60 ^[2]	

NOTES:

1. Represent standard ECG values of PCI for HV studies.
2. Represent further subdivisions of ECG values for analysis.

12.6.2. Vital Signs

Vital Sign Parameter (Absolute)	Units	Potentially Clinically Important Range	
		Lower	Upper
Systolic Blood Pressure	mmHg	< 85	> 160
Diastolic Blood Pressure	mmHg	< 45	> 100
Heart Rate	bpm	< 40	> 110

12.7. Appendix 7: Division of Microbiology and Infectious Disease Adult Toxicity Tables for Adverse Event Assessment

12.7.1. Laboratory Values

Laboratory abnormalities will be graded according to the modified US National institute of Allergy and Infectious Disease Division of Microbiology and Infectious Diseases (DMID) criteria [DMID, 2007]. Laboratory results are converted to use SI units.

HEMATOLOGY				
	Grade 1	Grade 2	Grade 3	Grade 4
Hemoglobin	9.5 to 10.5 gm/dL	8.0 to 9.4 gm/dL	6.5 to 7.9 gm/dL	<6.5 gm/dL
Absolute Neutrophil Count	1000 to 1500 /mm ³	750 to 999 /mm ³	500 to 749 /mm ³	<500 /mm ³
Platelets	75,000 to 99,999 /mm ³	50,000 to 74,999 /mm ³	20,000 to 49,999 /mm ³	<20,000 /mm ³
White Blood Cells	11,000 to 13,000 /mm ³	13,000 to 15,000 /mm ³	15,000 to 30,000 /mm ³	>30,000 or <1000 /mm ³
% Polymorphonuclear Leukocytes + Band Cells	>80%	90 to 95%	>95%	N/A
Abnormal Fibrinogen	Low: 100 to 200 mg/dL High: 400 to 600 mg/dL	Low: <100 mg/dL High: >600 mg/dL	Low: <50 mg/dL High: N/A	Fibrinogen associated with gross bleeding or with disseminated coagulation
Fibrin Split Product	20 to 40 mcg/mL	41 to 50 mcg/mL	51 to 60 mcg/dL	>60 mcg/dL
Prothrombin Time (PT)	1.01 to 1.25 × ULN	1.26 to 1.5 × ULN	1.51 to 3.0 × ULN	>3 × ULN
Activated Partial Thromboplastin (APTT)	1.01 to 1.66 × ULN	1.67 to 2.33 × ULN	2.34 to 3 × ULN	>3 × ULN
Methemoglobin	5.0 to 9.9%	10.0 to 14.9%	15.0 to 19.9%	>20%

N/A=not applicable; ULN=upper limit of normal.

CHEMISTRIES				
	Grade 1	Grade 2	Grade 3	Grade 4
Hyponatremia	130 to 135 mEq/L	123 to 129 mEq/L	116 to 122 mEq/L	<116 mEq/L or abnormal sodium with mental status changes or seizures
Hypernatremia	146 to 150 mEq/L	151 to 157 mEq/L	158 to 165 mEq/L	>165 mEq/L or abnormal sodium with mental status changes or seizures
Hypokalemia	3.0 to 3.4 mEq/L	2.5 to 2.9 mEq/L	2.0 to 2.4 mEq/L or intensive replacement therapy of hospitalization required	<2.0 mEq/L or abnormal potassium with paresis, ileus, or life-threatening arrhythmia
Hyperkalemia	5.6 to 6.0 mEq/L	6.1 to 6.5 mEq/L	6.6 to 7.0 mEq/L	>7.0 mEq/L or abnormal potassium with life-threatening arrhythmia
Hypoglycemia	55 to 64 mg/dL	40 to 54 mg/dL	30 to 39 mg/dL	<30 mg/dL or abnormal glucose with mental status changes or coma
Hyperglycemia (nonfasting and no prior diabetes)	116 to 160 mg/dL	161 to 250 mg/dL	251 to 500 mg/dL	>500 mg/dL or abnormal glucose with ketoacidosis or seizures
Hypocalcemia (corrected for albumin)	8.4 to 7.8 mg/dL	7.7 to 7.0 mg/dL	6.9 to 6.1 mg/dL	<6.1 mg/dL or abnormal calcium with life-threatening arrhythmia or tetany
Hypercalcemia (corrected for albumin)	10.6 to 11.5 mg/dL	11.6 to 12.5 mg/dL	12.6 to 13.5 mg/dL	>13.5 mg/dL or abnormal calcium with life-threatening arrhythmia
Hypomagnesemia	1.4 to 1.2 mEq/L	1.1 to 0.9 mEq/L	0.8 to 0.6 mEq/L	<0.6 mEq/L or abnormal magnesium with life-threatening arrhythmia
Hypophosphatemia	2.0 to 2.4 mg/dL	1.5 to 1.9 mg/dL or replacement Rx required	1.0 to 1.4 mg/dL intensive therapy or hospitalization required	<1.0 mg/dL or abnormal phosphate with life-threatening arrhythmia
Hyperbilirubinemia (when accompanied by any increase in other liver function test)	1.1 to <1.25 × ULN	1.25 to <1.5 × ULN	1.5 to 1.75 × ULN	>1.75 × ULN
Hyperbilirubinemia (when other liver function tests are in the normal range)	1.1 to <1.5 × ULN	1.5 to <2.0 × ULN	2.0 to 3.0 × ULN	>3.0 × ULN
Blood urea nitrogen	1.25 to 2.5 × ULN	2.6 to 5 × ULN	5.1 to 10 × ULN	>10 × ULN
Hyperuricemia (uric acid)	7.5 to 10.0 mg/dL	10.1 to 12.0 mg/dL	12.1 to 15.0 mg/dL	>15.0 mg/dL
Creatinine	1.1 to 1.5 × ULN	1.6 to 3.0 × ULN	3.1 to 6.0 × ULN	>6 × ULN or dialysis required

Rx=therapy; ULN=upper limit of normal.

ENZYMES				
	Grade 1	Grade 2	Grade 3	Grade 4
Aspartate aminotransferase (AST)	1.1 to <2.0 × ULN	2.0 to <3.0 × ULN	3.0 to 8.0 × ULN	>8.0 × ULN
Alanine aminotransferase (ALT)	1.1 to <2.0 × ULN	2.0 to <3.0 × ULN	3.0 to 8.0 × ULN	>8.0 × ULN
Gamma to glutamyl transferase (GGT)	1.1 to <2.0 × ULN	2.0 to <3.0 × ULN	3.0 to 8.0 × ULN	>8.0 × ULN
Alkaline Phosphatase	1.1 to <2.0 × ULN	2.0 to <3.0 × ULN	3.0 to 8.0 × ULN	>8.0 × ULN
Amylase	1.1 to 1.5 × ULN	1.6 to 2.0 × ULN	2.1 to 5.0 × ULN	>5.1 × ULN
Lipase	1.1 to 1.5 × ULN	1.6 to 2.0 × ULN	2.1 to 5.0 × ULN	>5.1 × ULN

ULN=upper limit of normal.

URINALYSIS				
	Grade 1	Grade 2	Grade 3	Grade 4
Proteinuria	1+ or 200 mg to 1 gm loss/day	2 to 3+ or 1 to 2 gm loss/day	4+ or 2 to 3.5 gm loss/day	Nephrotic syndrome or >3.5 gm loss/day
Hematuria	Microscopic only <10 RBC/hpf	Gross, no clots >10 RBC/hpf	Gross, with or without clots, or red blood cells casts	Obstructive or required transfusion

HPF=high powered field; RBC=red blood cells.

